Six Minute Walk Test (6MWT) ^b		X	X		X
Neuroimaging (MRI)					
Blood Draw		X	X		
Falls Calendar ^c		X	X	X	X

94 ^aTesting included in the ADAS-Cog plus95 ^bThis test may be completed at the gym facility on the first day of intervention96 ^cCalendar will be given to participant to complete and will be submitted to Research Staff at exercise training97

7. Determination of Sample Size

98 Sample size calculation is based on changes in our primary outcome: global cognitive
 99 function measured using the Alzheimer Disease Assessment Scale Cognitive 13 and

100 the plus variant (ADAS-Cog 13 and plus). A target sample of 200 participants (40 per
 101 arm) was determined based on 80% power to detect either main effects or an
 102 interaction of at least a moderate (Cohen's $d \sim 0.5$)¹ effect size of changes in the ADAS-
 103 Cog-13.² The final sample size accounted for a 15% attrition.

104

105 **8. Primary Outcomes**

106 Primary outcome will be changes in cognitive function measured with the ADAS-Cog 13
 107 items (ADAS-Cog-13) and the plus variant (ADAS-Cog-plus) at endpoint, 6 Month.
 108 Improvement at endpoint in either variant is considered evidence of efficacy.

109 **8.1 Change in cognitive function on ADAS-Cog-13 at post-intervention (Month 6)**

110 The ADAS-Cog 13 consists of 13 brief cognitive tests assessing memory, language,
 111 attention, concentration and praxis. The individual tests are listed in Table 2. Scores
 112 range from 0 to 84, with higher scores indicating severe cognitive impairment.

113 **8.2 Change in cognitive function on ADAS-Cog-Plus at post-intervention (Month 6)**

114 Four additional tests focusing on executive function will be added to the ADAS-Cog 13
 115 to comprise the plus variant³ (Table 2). Scores will be transformed into an algorithm
 116 validated by Crane et al.⁴ The higher scores will indicate severe of cognitive impairment.

117
 118 Table 2. Individual tests included in the ADAS-Cog

ADAS-Cog-13	ADAS-Cog-Plus
Word recall	Word recall
Delayed word recall	Delayed word recall
Following commands	Following commands
Constructional praxis	Constructional praxis
Ideational praxis	Ideational praxis
Naming objects	Naming objects
Orientations	Orientations
Word recognition	Word recognition
Remembering instructions	Remembering instructions
Comprehension	Comprehension
Word finding	Word finding
Spoken language	Spoken language
Number cancellation	Number cancellation
	Trial Making A and B
	Digit symbol substitution

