153 AP/PA correction scan = 7 min) to calculate fractional anisotropy and diffusivity in white
154 matter tracts as well as derive tract-based statistics. Cerebrovascular integrity and
155 pathology will be assessed using the following contrasts: PD/T2 = 5 min; FLAIR = 7 min,
156 and T2* = 5 min). Functional magnetic resonance imaging at rest (rsfMRI plus field map
157 = 12 min) will also be acquired to measure change in data-driven functional networks.

158 **9.5 Change in Blood biomarkers measures**

159 Serum biomarkers of inflammation (C reactive protein, and interleukin 6), neuroplasticity
160 (brain-derived neurotropic factor), endothelial health (vascular endothelial growth factor
161 1), and vitamin D serum levels will be measured before and after intervention.

162 **9.6 Covariates**

163 Pre-specified covariates will be age, sex, years of education and number of
164 comorbidities.

165

166 **10. Statistical Analysis**

167 **10.1 Descriptive Analysis**

168 The baseline characteristics will be summarized using means and standard deviation, or
169 medians and interquartile range where appropriate, for continuous characteristics, and
170 frequencies and percentages for categorical variable.

171 **10.2 Primary Efficacy Analysis**

172 The primary analysis will be based on the intention-to-treat principle, including everyone
173 who were randomized. Comparisons between arms will be conducted according to pre-
174 specifications in the protocol. These comparisons align well with the recommended
175 analysis and reporting of factorial trials⁵, which used “inside the table” and “at the
176 margin” analyses for different comparisons. The “inside the table” analysis will be used
177 to compare each intervention effect to control, while “at the margins” analysis will be
178 used to assess the effect of adding intervention.

179 The major interest would be the effect of the intervention on change in primary
180 outcomes at 6 Month compared to the control arm (arm 5). The primary outcome
181 measure of mean change in ADAS-Cog-13 and ADAS-Cog-Plus scores will be analyzed
182 using a linear mixed model with restricted likelihood estimation. The model will be fitted
183 with participant-specific random intercept and fixed effects of time, intervention arm, and
184 time x intervention arm interaction. The time variable will be used as a categorical
185 variable (0 = baseline; 1 = Month 6.) The intervention arm variable will be dummy

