186 coded, using the control group as a reference category. The interaction term will be

187 used to assess between-group differences (representing a mean difference in change in
188 cognitive scores over time between two groups). With dummy coding of the intervention
189 arm, the interaction term will allow to compare the mean change in each intervention
190 arm to the arm 5 (control). The within-group difference (representing a mean change in
191 cognitive scores over time within the group) will be measured with marginalized mean
192 from the linear mixed regression model. The model will be further adjusted for
193 participant characteristics including age, sex, education, and comorbidities.

194 An unstructured covariance matrix will be used for all models. The model assumption
195 will be assessed using the normal quantile plots of residuals for normality and the
196 residuals vs. fitted plot for variance homogeneity. If the assumptions are not fully met,
197 the data will be transformed (i.e., log). Missing data will not be imputed and will be
198 assumed to be missing at random, as the mixed model approach is well-known to
199 handle such data effectively.⁶ The baseline data from individuals who did not complete
200 Month 6 assessment will be included in the linear mixed model.

201 The mean difference between groups will be presented with their 95% CI and p-value,
202 while the mean change within group will be presented with their standard error. The
203 obtained marginalized mean and standard deviation will be used to calculate the effect
204 size (
$$\frac{\text{mean change in treatment } X - \text{mean change in treatment } Y}{\text{pooled standard deviation of change}}$$
). As outlined in our published
205 protocol, we will calculate the proportion of participants with improvement in primary
206 outcomes.

207 All tests will be two-sided, and p-value of less than 0.05 will be considered as
208 statistically significant. Adjustments for multiple comparisons will not be made as the
209 trial is intended to compare the intervention effect to the control rather than pairwise.⁷
210 Per-protocol analysis will be performed as well.

211 As per recommended analyses of fractional factorial design⁸, “at the margin” analyses
212 will be performed by collapsing arms according to the pre-specified comparison.
213 Collapsing intervention arms allow to increase the study power to detect the difference

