214 in effect. More details are provided below for each pre-specified comparison.

215 10.2.1 Effect of aerobic-resistance exercise

216 To address objective 1 (the effect of supervised aerobic-resistance exercise on
217 cognitive function), the intervention arms providing exercise intervention (arm 1 to 4) will
218 be collapsed as one category and compared to the control (arm 5). The new
219 independent variable will be created to represent exercise intervention: aerobic-
220 resistance exercise intervention (collapsed arm 1 to 4), and control exercise intervention
221 – BAT – (arm 5). The new intervention variable will be fitted into the same linear mixed
222 model described above. Using the interaction between exercise intervention x time, the

223 change in primary outcome will be contrasted between participants receiving the
224 aerobic-resistance exercise and those not receiving the aerobic-resistance exercise.

225 10.2.2 Effect of adding cognitive training

226 The objective 2 (the effect of adding cognitive training to aerobic-resistance exercise on
227 cognitive function) will be examined by pooling the intervention arms providing both
228 exercise and cognitive intervention (arm 1 and 2) and pooling the intervention arms
229 providing exercise intervention but not cognitive intervention (arm 3 and 4). A new
230 independent variable will be created for addition of cognitive training: both exercise and
231 cognitive intervention (pooled arm 1 and 2) and exercise but no cognitive intervention
232 (pooled arm 3 and 4). Using the interaction term in the linear mixed model, the contrast
233 will be made between the two collapsed arms to assess whether the effect of adding
234 cognitive training to aerobic-resistance exercise differ from aerobic-resistance exercise.
235 If there is a significant difference observed, the two collapsed arms will be compared to
236 the control arm (arm 5). This marginal analysis will allow to evaluate the main effect of
237 aerobic-resistance exercise alone (pooled arm 1 and 2) and aerobic-resistance exercise
238 with cognitive training (pooled arm 3 and 4) compared to the control (arm 5) with higher
239 power (as a result of increase in sample size).^{5,8}

240 10.2.3 Effect of adding vitamin D supplements

241 The objective 2 (the effect of adding vitamin D to aerobic-resistance exercise on
242 cognitive function) will be examined by pooling the intervention arms providing both

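### SAP section 7's 80% power at d of about 0.5 is met for the cognitive training and vitamin D margins (82%) but not for exercise (74%), and does not carry over to comparisons of one arm or one pair of arms with arm 5 (53% and 65%)

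*Combined protocol and SAP*

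**What the plan says.** SAP section 7 sets 200 participants, 40 per arm. It says the number "was determined based on 80% power to detect either main effects or an" interaction, at an effect of about 0.5 SD of change in ADAS-Cog-13, and adds: "The final sample size accounted for a 15% attrition". It does not say which contrast was used.

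SAP section 10.2 then plans contrasts of different sizes:

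- **Each arm against arm 5.** The section introduces this with "The major interest would be the effect of the intervention on change in primary" outcomes against the control arm. Objective 4 (section 10.2.4) is arm 1 against arm 5.
- **Exercise, Objective 1 (10.2.1).** Arms 1 to 4 will "be collapsed as one category and compared to the control (arm 5").
- **Cognitive training (10.2.2) and vitamin D (10.2.3).** Two arms are set against two arms. A follow-up is planned: "If there is a significant difference observed, the two collapsed arms will be compared to" arm 5. Section 10.2.3 has the same step.

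Tests are two-sided at 0.05. On multiplicity, the SAP says "Adjustments for multiple comparisons will not be made as the" aim is comparison with control.

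Protocol section 5.3 has a separate calculation. Its text gives 34 per arm for 80% power, adjusted for 10 pairwise comparisons. Its table puts 34 in the column for Type I error 0.05.

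**The concern.** One power figure is attached to a design whose planned contrasts range from 34 vs 34 to 136 vs 34. With equal allocation to five arms, only the two-against-two margins use four arms in balance. Exercise uses all five arms, but its precision is limited by the 34 controls. Comparisons of one arm or one pair with arm 5 rest on fewer people still.

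Section 7 is the SAP's only power statement. If its 80% is taken as the design power of the exercise test, a null result for Objective 1 is read a little too firmly. If it is carried over to Objective 4, a null result there is read much too firmly.

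**Working it through.** **Inputs.** 40 per arm, d of about 0.5 in change and 15% attrition (SAP section 7); 1:1:1:1:1 allocation (SAP section 4); two-sided 0.05 without adjustment (SAP section 10.2). Completers per arm: 40 × 0.85 = 34.

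**Method.** In SD units of change, SE = √(1/n₁ + 1/n₂), the noncentrality is 0.5/SE, and power is the upper tail of the noncentral t with n₁ + n₂ − 2 degrees of freedom beyond the two-sided 5% critical value. The other tail is negligible. The detectable effect is the d that gives 80%.

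**The plan's figure first.** For a two-against-two margin, 80% at d = 0.5 needs 64 per side, or 32 completers per arm. 32/0.85 = 37.6, so 38 recruited per arm, against 40 planned. The stated 80% is therefore met for these margins.

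**Per contrast, 34 completers per arm:**

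| Contrast | n | SE | 0.5/SE | Power | Detectable at 80% |
|---|---|---|---|---|---|
| Cognitive training margin; vitamin D margin | 68 vs 68 | 0.171 | 2.92 | 82.5% | 0.48 SD |
| Exercise (Objective 1) | 136 vs 34 | 0.192 | 2.61 | 73.7% | 0.54 SD |
| Collapsed pair vs arm 5 | 68 vs 34 | 0.210 | 2.38 | 65.5% | 0.59 SD |
| Arm 1 (Objective 4) or any single arm vs arm 5 | 34 vs 34 | 0.243 | 2.06 | 52.9% | 0.69 SD |

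Completers per arm needed for 80% at d = 0.5 are 32, 40, 48 and 64 in the same order.

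**Attrition.** Exercise power at 0, 5, 10 and 15% attrition is 80.4, 78.3, 76.1 and 73.7%. It reaches 80% only at 160 vs 40, which leaves nothing for the attrition that section 7 says is covered. A single arm vs arm 5 has 59.8% even with no attrition.

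**Dropouts' baselines kept in the mixed model.** SAP section 10.2 says that the baseline data of people without the "Month 6 assessment will be included in the linear mixed model". With 40 baselines and 34 completers per arm, the effective number per arm for change is 2/[(1 + r)/34 + (1 − r)/40], where r is the correlation between baseline and month 6. The documents do not give r, so a range is assumed: 34.3 at r = 0.9, 35.3 at r = 0.5 and 36.8 at r = 0. Exercise power then runs from 74.0 to 76.9%, and single-arm power from 53.2 to 56.1%.

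**Interaction.** Section 10.2 uses the word only for time by arm and time by collapsed-arm terms. These are the contrasts in the table. No cognitive training by vitamin D test is planned, and section 7 gives no scale. The scale matters: for such a test, SE = √(4/34) = 0.343, and power is about 30% if 0.5 SD is the full difference of differences but 82% if it is half of that.

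**Protocol section 5.3.** Adjusting 0.05 for 10 comparisons by Bonferroni gives 0.005. The text attaches 34 to an adjusted level and the table attaches it to 0.05. The SD of 3 is that of a score, and no SD of change is given.

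**The case against.** **Section 7 promises 80% only for main effects or an interaction.** This stands for Objective 4. A reader might infer that section 7 overstates its power by the gap between 80% and 53%. The documents do not support that, because section 7 makes no express statement about one arm against arm 5, and section 10.2 keeps those comparisons apart from the marginal ones. What can be said is that section 7 is silent and the 80% does not carry over. The SAP's vocabulary makes the slip easy: sections 10.2.2 and 10.2.3 call the comparison of collapsed pairs with arm 5 a main effect, and section 10.2.4 tests Objective 4 through an interaction term. The objection does not rescue exercise, which is a main effect on any reading.

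**The effect size is only approximate.** This has force for exercise, where 80% is reached at 0.54 SD. It does not stretch to 0.69 SD.

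**The model recovers power.** Retained baselines lift exercise to at most 76.9%. Age, sex, education and comorbidities enter as adjustments fixed over time, with no stated interaction with time, so they do not reduce the variance of within-person change.

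**Success can come from either outcome.** SAP section 8 says: "Improvement at endpoint in either variant is considered evidence of efficacy". If both variants carry a 0.5 SD effect and their changes correlate between 0.95 and 0.5 (both assumed), simulation gives at least one significant exercise result in 77.8 to 87.1% of trials. The false-positive chance then rises to between 6.4 and 9.0%. Section 7 names ADAS-Cog-13 alone, so this narrows the gap without closing it.

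**The planned confidence intervals will show precision.** They will, but they do not correct a stated design property.

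**Conclusion.** The point holds for exercise as an error in the stated figure, and for the comparisons with arm 5 as an omission. At 0.5 SD, exercise has 74% rather than the stated 80%, a modest gap. Single arms and collapsed pairs against arm 5 have 53% and 65%, which section 7 does not report. The two margins meet the claim at 82%.

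These are per-test figures on ADAS-Cog-13. They assume 34 completers in every arm, equal variance of change, no covariate gain and an unadjusted two-sided 0.05. Section 7 states no alpha, so that level is taken from section 10.2.

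Three stronger readings are not supported:

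- **That the 80% was calculated for the two margins.** No section says so. The 40 per arm also equals 34/0.85 from protocol section 5.3, and 200 completers is what exercise would need.
- **That the SAP claims power for a cognitive training by vitamin D interaction it cannot deliver.** The term is undefined and no such test is planned.
- **That 34 per arm is too few on the protocol's own assumptions.** Protocol section 8 plans ANCOVA on baseline. With 3 points and an SD of 3, this needs at most 17 per arm at 0.05 and 29 at 0.005. The fault there is the mismatch between text and table.

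**What to change.** Keep N = 200, the model and the comparisons. In SAP section 7:

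- Say that 80% power is met for the cognitive training and vitamin D margins. Do not say that the 80% refers to them.
- List power and detectable effect per test on ADAS-Cog-13, at 34 completers per arm, d = 0.5 in change and unadjusted two-sided 0.05: cognitive training 82%, 0.48 SD; vitamin D 82%, 0.48 SD; exercise 74%, 0.54 SD; collapsed pair vs arm 5 65%, 0.59 SD; arm 1 or any single arm vs arm 5 53%, 0.69 SD.
- Define the test and scale meant by interaction, or delete the phrase.

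Separately, in protocol section 5.3, state the alpha and the SD to which 34 per arm belongs, so that text and table agree.

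The cost is wording only. The downside is that the stated power becomes less favourable for exercise and is shown to be low for the single-arm comparisons, including Objective 4.

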243 exercise and vitamin D intervention (arm 1 and 3) and pooling the intervention arms
244 providing exercise intervention but not vitamin D (arm 2 and 4). A new independent
245 variable will be created to represent addition of vitamin D: both aerobic-resistance
246 exercise and vitamin D intervention (pooled arm 1 and 3) and aerobic-resistance
247 exercise but no vitamin D intervention (pooled arm 2 and 4). The linear mixed model will
248 be repeated using this new independent variable and the two pooled arms will be
249 compared. This will allow to explore whether adding vitamin D to aerobic-resistance
250 exercise improve the outcome compared to the aerobic-resistance exercise. If a
251 significant difference is observed, the two pooled arms will be compared to the control
252 arm (arm 5) to assess the main effect.

253 10.2.4 Effect of multidomain intervention

254 The objective 4 (effect of multi-domain intervention (aerobic-resistance exercise +
255 cognitive training + Vitamin D supplement) on cognitive function) will be assessed using
256 the time x intervention arm interaction fitted in the linear mixed model in section 10.2.
257 The interaction term between time x intervention arm 1 will represents the effect of
258 multidomain intervention (arm 1) compared to the control (arm 5).

259 **10.2.5 Long-term effect: From Baseline and Post-intervention to Follow up**

260 The long-term intervention effect from baseline and post-intervention to follow-up
261 (Month 12) will be assessed using the linear mixed model. Time will be used as a
262 categorical variable (Baseline, Month 6, and Month 12). Individuals with incomplete
263 follow up assessments will still be included in the linear mixed model.

264 **10.2.6 Post-hoc analyses**

265 ADAS-Cog-Plus is a construction proposed originally by Skinner et al.⁹, adding extra
266 tests for executive function and verbal fluency to increase sensitivity to detect
267 progression from MCI to dementia. Post hoc analyses will be performed to explore the
268 effect of intervention on ADAS-Cog-Plus scores by adding individual Plus items, one by
269 one, to ADAS-Cog-13.

270 **10.3 Secondary Outcomes Analyses**

271 The secondary analysis will be performed in an intention-to-treat population and a per-
272 protocol population. The details of the statistical analysis plan for secondary outcomes
273 are not included in this analysis plan as the secondary outcome analyses will not be

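### SAP 8 counts improvement on either of two primary scales as efficacy, each at an unadjusted 0.05; the reason given for no adjustment concerns arms, and the protocol names one scale

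*Combined protocol and SAP*

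**What the plan says.** **SAP 8** defines the primary outcome as change at Month 6 on two scales, ADAS-Cog-13 and ADAS-Cog-Plus, and gives the success rule: "Improvement at endpoint in either variant is considered evidence of efficacy". SAP 8.2 describes how the second scale is built: "Four additional tests focusing on executive function will be added to the ADAS-Cog 13". Its score is then transformed. Table 2 of the SAP lists all 13 items of the first scale inside the second.

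**SAP 10.2** makes every test two-sided at 0.05. On multiplicity, two consecutive lines read "Adjustments for multiple comparisons will not be made as the" and "trial is intended to compare the intervention effect to the control rather than pairwise".

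**SAP 7** states its 80% power and its effect size of about d = 0.5 for change in ADAS-Cog-13.

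**The protocol** names ADAS-Cog Plus as the primary scale in hypothesis 1 (section 2.1.a), in section 4.1 and in section 8. Section 8 also lists a dichotomised ADAS-Cog Plus result as primary, which is another form of the same scale. For multiplicity, section 8 refers to Tukey comparisons and says that Hochberg's version of Bonferroni determines significance. It defines no family of tests for Hochberg.

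**The concern.** An either-scale rule gives each treatment contrast two chances of success. With each chance taken at the full 0.05, the contrast no longer has the error rate that the SAP states. The SAP's only argument against adjustment is about which arms are compared. It would read the same if there were one scale or ten, so it cannot justify leaving the two-scale rule unadjusted.

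The rule also allows efficacy to be claimed on ADAS-Cog-13 alone, a scale that the protocol does not name as primary. The SAP gives no reason for adding it as a second primary scale.

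**Working it through.** **Inputs**
- Two-sided 0.05 per test, no adjustment: SAP 10.2. In the direction of improvement this is 0.025.
- Success on either scale: SAP 8.
- 40 per arm with 15% attrition: SAP 7 and protocol 5.3. 40 × 0.85 = 34 evaluable per arm, and 5 × 40 = 200.
- d of about 0.5, stated for ADAS-Cog-13: SAP 7. Applying it to ADAS-Cog-Plus is an assumption.
- Correlation r between the two scales' estimated change contrasts: **not given**. Values of 0.7 to 0.9 are assumed, with a wider range shown. The shared 13 items make a high value plausible.

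**Step 1. The plan's own figure.** With one scale, P(|Z| > 1.96) = 0.05 and P(Z > 1.96) = 0.025. The stated level reproduces.

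**Step 2. The either-scale rule, no effect on either scale, one contrast.**
Improvement direction: P = 1 − Φ₂(1.96, 1.96; r), where Φ₂ is the bivariate normal distribution function.
Both directions: P = 1 − P(|Z₁| ≤ 1.96 and |Z₂| ≤ 1.96).
As a check on the ends, r = 0 gives 1 − 0.975² = 4.94% and r = 1 gives 2.5%.

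| r (assumed) | False improvement (nominal 2.5%) | Either direction (nominal 5%) |
|---|---|---|
| 0.5 | 4.5% | 9.1% |
| 0.7 | 4.2% | 8.4% |
| 0.8 | 3.9% | 7.8% |
| 0.9 | 3.5% | 7.0% |
| 0.95 | 3.2% | 6.5% |
| 0.98 | 3.0% | 5.9% |

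Relative to nominal: 4.17/2.5 = 1.7 at r = 0.7, 3.52/2.5 = 1.4 at r = 0.9, and 3.0/2.5 = 1.2 at r = 0.98. A simulation with five arms of 34 and a pooled covariance on 170 − 5 = 165 df agrees to within 0.1 point.

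**Step 3. Hochberg on the two p-values within one objective.** Claim both scales if the larger p is at most 0.05; otherwise claim the scale with the smaller p if that p is at most 0.025. False improvement is 2.3%, 2.2% and 2.1% at r = 0.7, 0.8 and 0.9. In either direction it is 4.6%, 4.4% and 4.2%.

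**Step 4. Power at d = 0.5.** Noncentral t on 165 df, with λ = d × √(n₁n₂/(n₁ + n₂)). The 0.025 column is the worst case for Hochberg, in which the other scale never helps.

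| Objective | Groups | λ | At 0.05 | At 0.025 |
|---|---|---|---|---|
| 1 | 136 v 34 | 0.5 × √27.2 = 2.61 | 74% | 64% |
| 2 and 3 | 68 v 68 | 0.5 × √34 = 2.92 | 83% | 74% |
| 4 | 34 v 34 | 0.5 × √17 = 2.06 | 54% | 42% |

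If both scales truly have d = 0.5 and r is 0.7 to 0.9, Hochberg keeps about 70%, 80% and 49% on a given scale. Under the same assumption, the chance of a claim on at least one scale is:

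| Objective | Either rule | Hochberg | One scale |
|---|---|---|---|
| 1 | 84%–80% | 77%–73% | 74% |
| 2 and 3 | 91%–87% | 86%–82% | 83% |
| 4 | 66%–61% | 57%–52% | 54% |

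**Step 5. Arm 1 against arm 5 at larger effects.** The protocol's target is 3 points. Its SD of 3 (section 5.3) accompanies a mean score, and the SD of change is not given. If the SD of change is 3√2 = 4.24, then d = 3/4.24 = 0.71, and power falls at most from 82.6% to 74.3%. If it is 3, then d = 1.0, and power falls at most from 98.4% to 96.8%.

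**The case against.** The strongest reply is that the inflation is small and its size is assumed. One scale contains the other, so r could be 0.95 or more, and the excess would then be 0.7 point or less. The trial is labelled Phase II, and the protocol treats a significant result as only preliminary support for efficacy. All of this stands. It limits how serious the point is, but the excess is zero only at r = 1, and four added executive tests with a transformed score make the two scales different measures.

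A reader might also infer more than the documents support:

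- **That leaving arms and objectives unadjusted is itself an error.** The SAP's reason fits objectives 2 and 3 poorly, since each first compares pooled exercise arms with each other and brings in arm 5 only afterwards: "If there is a significant difference observed, the two collapsed arms will be compared to" the control arm. But the four objectives ask distinct questions, and not adjusting across them is defensible in a Phase II factorial trial.
- **That the protocol sets a fixed, stricter cut-off through Tukey.** It does not. Tukey there depends on a significant within-group comparison, and the same section says Hochberg determines significance. That sentence stands in a paragraph that opens with secondary analyses, so even its scope is unclear.
- **That the SAP promises the protocol's primary scale and then departs from it.** Its statement about following pre-specifications covers comparisons between arms only. The SAP also relies on a published protocol that is not among the documents.
- **That power is hardly affected because the protocol assumes d = 1.0.** That reading takes the SD of a score as the SD of change.

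**Conclusion.** The point holds for the two-scale rule and for the mismatch on the primary scale. Under SAP 8 and 10.2 together, the chance of a false improvement claim on one contrast is above the nominal 2.5% at any correlation below 1. It is about 4.2% to 3.5% at assumed correlations of 0.7 to 0.9, and 3.2% to 3.0% at 0.95 to 0.98. These figures assume no effect on either scale and approximately normal test statistics, and they are per contrast. Their exact size rests on a correlation that the documents do not give. The SAP's argument against adjustment does not cover this rule, and the SAP and the supplied protocol disagree on how many primary scales there are. This should be fixed; it does not by itself undermine the trial.

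**What to change.** Delete the unadjusted either-scale sentence in SAP 8 and choose one rule:

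- **(a) One scale.** Keep the protocol's ADAS-Cog Plus (continuous change at 6 months) as the single primary and make ADAS-Cog-13 secondary. Restate SAP 7 for that scale.
- **(b) Two scales.** Keep both and apply Hochberg to the two p-values within each objective.

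Then reconcile SAP 8 and 10.2 with protocol sections 4.1 and 8 on the primary scale and the multiplicity method, including what Hochberg applies to and the status of the dichotomised result. State plainly whether the four objectives are treated as separate questions.

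**Cost.** Wording, a few lines of code and some power. Under (b) the worst-case loss per scale at d = 0.5 is 9 to 12 points, depending on the objective. For arm 1 against arm 5 it is about 8 points at d = 0.71 and under 2 points at d = 1.0. Option (a) tests at the full 0.05, so it has no per-test loss if d = 0.5 also holds for ADAS-Cog Plus, but it gives up the second chance of a claim.
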